## IV.case selection

### 4.1 inclusion criteria

- ( 1 ) Patients with depressive symptoms after papillary thyroid carcinoma surgery in the outpatient department of Zhejiang Cancer Hospital ( patients with depressive symptoms by clinical psychiatrist and Hamilton Depression Scale score of 8-20 points ) ;
- ( 2 ) Han nationality ;
- ( 3 ) no previous depression and other mental diseases ;
- ( 5 ) 18-80 years old ;
- ( 6 ) Women ;
- ( 8 ) BMI : 19 ~ 24. ( BMI calculation method :  $BMI = \text{weight ( kg )} / \text{height}^2$  ( m ) )

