### 4.2 excluded criteria

- ( 1 ) suffering from other diseases of the intestinal system ;
- ( 2 ) Have received gastrointestinal surgery before intervention ;
- ( 3 ) Including patients with other malignant tumors, who need chemotherapy, radiotherapy, biological therapy or traditional Chinese medicine treatment ;
- ( 4 ) received antibiotics or microecological modulators within 3 months before the intervention ;
- ( 5 ) Acute intestinal obstruction ;
- ( 6 ) Patients with severe depressive symptoms who must receive antidepressant treatment ;
- ( 7 ) organic diseases such as heart and brain diseases, brain trauma ;
- ( 8 ) history of mental illness, use of psychoactive drugs such as drugs ;
- ( 9 ) Severe liver and kidney dysfunction ;
- ( 10 ) Pregnancy, lactation

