## VI.drug combination

It is forbidden to use any interfering drugs, such as biological therapy, traditional Chinese medicine treatment, antibiotic treatment, microecological modulators, antidepressants, other health care products with immune regulation function,

---

psychotropic drugs and so on.

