## **VIII.response evaluation criteria**

### 8.1 leading indicator

#### ( 1 ) Hamilton Depression Scale ( HAMD-24 ) score classification

No obvious depressive symptoms : total score 0-7 points ; may have depression : total score 8-20 points ; mild or moderate depression : total score 21-35 ; severe depression : total score 36-76 points.

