## **X. Statistical analysis of test data**

### **1. Data Selection for Statistical Analysis**

( 1 ) Full Analysis Set ( FAS ) : Constituted of all cases with depressive symptoms after papillary thyroid carcinoma surgery that were randomized into groups and at least 1 month after surgery, that is, Intention-to-treat. The FAS set was used for efficacy analysis, and the missing data was filled with the last observed data filling ( LOCF ) criterion.

( 2 ) Per-Protocol Set ( PPS ) : PPS is composed of all cases that meet the test plan, have good compliance, do not use prohibited drugs during the test, and complete the content of CRF requirements. The PPS set is used for efficacy analysis.

( 3 ) Safety Analysis Set ( SAS ) : It is composed of all cases that have been randomly grouped, used at least one drug and have safety evaluation. The SAS set is used for safety analysis.

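### Starting an antidepressant removes a patient from the per-protocol efficacy set, and no rule says how that patient's HAMD-24 scores enter the full analysis set

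*Combined protocol and SAP*

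**What the plan says.** - **Prohibited drugs.** Section VI states "It is forbidden to use any interfering drugs" and names antidepressants and psychotropic drugs among them.
- **PPS.** Section X.1(2) admits only patients who, among other conditions, "do not use prohibited drugs during the test". It adds "The PPS set is used for efficacy analysis" and does not say that this analysis is supportive.
- **FAS.** Section X.1(1) gives one data rule: "The FAS set was used for efficacy analysis, and the missing data was filled with the last observed data filling ( LOCF ) criterion". It says nothing about scores observed after a prohibited drug.
- **Endpoint.** Section 8.1(2) defines relief as any fall in HAMD score after 90 days, with no condition on other treatment. Section X.2(4) analyses scores by repeated measures or baseline-adjusted regression, and compares changes by t test.
- **Worsening.** Section IX counts deterioration of existing symptoms as an adverse event and has its treatment and outcome recorded. Section XI.3 allows emergency unblinding for deterioration that needs emergency measures and then treats the patient as a shedding case. Section 4.4 has general withdrawal rules. None of the three says how an antidepressant started after randomisation enters the efficacy analysis.

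**The concern.** In most trials a prohibited drug is a protocol deviation with no close tie to the outcome. Here the outcome is depression, so an antidepressant started because the patient got worse carries direct information about it. Removing that patient from an efficacy set is selection after randomisation that depends on the outcome. Keeping the patient with a score improved by the antidepressant can record relief under the study powder.

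If the powder prevents some patients from worsening, or causes some to worsen, part of that effect appears as a difference in starts between the arms. The PPS cannot show it, and the FAS may show only part of it.

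**Working it through.** The documents give no expected effect, standard deviation or rate of antidepressant use, so there is no figure of the plan's own to reproduce on this point. The arm sizes, 200 and 100, are from section 5.1. Everything else below is assumed.

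**Inputs.** Starters: 4% of active (8 of 200) and 10% of control (10 of 100). A starter is 6 points above baseline on worsening. All others fall by 4 points in both arms.

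**Formula.** Mean change in an arm = p × s + (1 − p) × (−4), where p is the share of starters and s is the change assigned to them. The active-minus-control difference is then (p_active − p_control) × (s + 4).

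| Handling of starters | Active | Control | Difference |
|---|---|---|---|
| Worsened score kept, s = +6 | 0.24 − 3.84 = −3.60 | 0.60 − 3.60 = −3.00 | −0.60 |
| Set to baseline, s = 0 (also LOCF from baseline) | −3.84 | −3.60 | −0.24 |
| LOCF from a day-28 change of −2, before worsening | −0.08 − 3.84 = −3.92 | −0.20 − 3.60 = −3.80 | −0.12 |
| Day 90 observed, starters brought to the others' level, s = −4 | −4.00 | −4.00 | 0 |
| PPS, starters removed | −4.00 | −4.00 | 0 |

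**Relief**, assuming 60% among non-starters:
- Starters counted as not relieved: 0.60 × 0.96 = 57.6% against 0.60 × 0.90 = 54.0%, a difference of +3.6 percentage points.
- PPS: 60% against 60%, a difference of 0.
- Every starter scored as relieved at day 90 after the antidepressant: 57.6 + 4 = 61.6% against 54.0 + 10 = 64.0%, a difference of −2.4 percentage points.

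**Range for the mean difference.**
- Starters 3% and 6%: −0.03 × 10 = −0.3 with worsened scores kept; −0.03 × 4 = −0.12 at baseline.
- Starters 5% and 15%: −0.10 × 10 = −1.0, and −0.10 × 4 = −0.40.
- Equal rates: 0 under every handling.
- Reversed rates (10% active, 4% control): +0.6 and +0.24, so a harm is hidden in the same way.
- PPS: 0 throughout.

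**The case against.** Excluding users of prohibited drugs is what a per-protocol set normally does, and the FAS keeps those patients. Using an observed day-90 score whatever else the patient took is an ordinary intention-to-treat approach, and X.1(1) labels the FAS that way. Both points stand. They are reasons to keep the conventional PPS, not to leave it unranked, and they do not make the FAS handling explicit. That approach also estimates the effect of powder plus any antidepressant, which the plan never says it intends.

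The plan would also show some signs of an imbalance. X.2(1) compares shedding and elimination rates by arm, and X.2(3), though hard to read, touches on banned drugs. X.2(5) compares adverse reactions, though worsening judged unrelated to the drug may not be counted there. These comparisons could reveal a difference in starts; none changes an efficacy result.

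Three stronger readings are tempting, and the documents do not support them:
- *That nothing covers worsening.* Sections IX, XI.3 and 4.4 do, for safety, unblinding and withdrawal. The gap is confined to the efficacy analysis.
- *That the effect is lost from both efficacy sets.* For the FAS this is inferred from silence. If the last score before a missing day 90 is a worsened day-28 value, LOCF carries it forward and the −0.6 is kept in full. It falls to 0 only if day 90 is scored and starters reach the others' level.
- *That the eligibility criteria conflict.* Exclusion 4.2(6), "Patients with severe depressive symptoms who must receive antidepressant treatment", may look pointless beside an entry range of "Hamilton Depression Scale score of 8-20 points" and the band "severe depression : total score 36-76 points". But 4.2(6) does not cite that band and may rest on clinical judgement. At most it is a harmless redundancy.

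**Conclusion.** The point holds in a limited form. That the PPS drops antidepressant starters follows directly from sections VI and X.1(2). That the FAS has no rule for their later scores is an omission, and its effect depends on whether day 90 is still scored, which the plan does not say.

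On the assumed inputs, a difference of −0.6 HAMD-24 points becomes 0 in the PPS and anything from −0.6 to 0 in the FAS, depending on which score is used. The rates are illustrative. Bias between arms needs starts, or their effect on scores, to differ by arm, and its direction cannot be known in advance. The documents define no treatment failure, so counting a start as one is an analysis choice that I recommend, not a rule the plan has broken. This is an inexpensive improvement and does not invalidate the planned analysis.

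**What to change.** 1. In X.1, keep the conventional PPS but state that it is supportive to the FAS.
2. In X.2(4), add an FAS analysis of relief that counts patients who start an antidepressant or psychotropic for worsening as not relieved. X.2(4) now names only analyses of scores, so this comparison has to be written in.
3. Add a sensitivity analysis of mean HAMD-24 in the FAS that sets a starter's day-90 score to the worse of baseline and the last score before the start. On the inputs above it gives −0.24 if no visit caught the worsening and −0.6 if one did, so it does not always recover the whole difference.
4. Report starts by arm, using the concomitant medication already recorded at both visits, and state whether day 90 is still scored after a start.

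The cost is a few sentences of SAP wording, the added analyses and slightly lower relief rates. No new data item is needed beyond noting that a start was for worsening.

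Separately, section VI forbids antidepressants while 4.4 does not name patients who come to need one during the 90 days. The two sections should be reconciled; the clinical rule is for the investigators.

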### **2. statistical analysis plan**

---

Statistical analysis was performed using SPSS 9.1.3 statistical software.

( 1 ) Distribution of two groups of cases : the comparison of the shedding and elimination rates of the two groups was performed by  $\chi^2$  test or exact probability method.

( 2 ) Comparability analysis : Demographic data and other basic indicators were compared to measure the comparability of the two groups. According to the type and distribution of data,  $\chi^2$  test or exact probability method, CMH test, t test, variance analysis or non-parametric statistical method were used.

( 3 ) Compliance analysis : To compare whether the two groups of patients use the test drugs on time and in quantity. The drugs that were not banned in the regimen were mainly tested by  $\chi^2$  test or exact probability method.

( 4 ) Validity analysis : Repeated measures were used to compare the differences in measurement data such as depression scores and sleep scores between the experimental group and the control group, or linear regression models were used to control baseline depression scores or sleep scores. Differences in depression scores and sleep scores between the two groups. Compare the score after the end of the experiment with the baseline score, calculate the difference before and after the change, and use the t test to compare the difference between the score changes of the experimental group and the control group.

( 5 ) Safety analysis : adverse reactions were statistically described, and the incidence of adverse reactions in the two groups was compared by  $\chi^2$  test or exact probability method.

( 6 ) All statistical tests should give test statistics and corresponding p values. When using the exact probability method, the p value is given directly.  $P \leq 0.05$  indicated that the difference was statistically significant.

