### **V.test scheme**

#### 5.1 Number of cases and distribution of cases

According to the ' Drug Registration Management Method ', the study sample should be no less than 100 pairs. It is assumed that the case shedding rate is 15 %, and the sample size is not less than 117 pairs. Finally, the sample size was determined to be 300 cases. In order to reduce the use of placebo in the control group, so that more patients benefit from treatment, the experimental group : the control group was assigned to 2 : 1, that is, 200 cases in the experimental group and 100 cases in the control group.

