## **VII.research process**

### 7.1 Screening / Baseline ( Week 0 )

- ( 1 ) Sign informed consent ;
- ( 2 ) Complete the verification of inclusion and exclusion criteria ;
- ( 3 ) to obtain demographic data and medical history data ;
- ( 4 ) Psychiatric examination and HAMD-24 scale evaluation ;
- ( 5 ) PSQI scale evaluation ;
- ( 6 ) Stool specimen collection ;
- ( 7 ) Thyroid function test residual blood collection ;
- ( 8 ) Women of childbearing age to do urine pregnancy test ;
- ( 9 ) Record the combined medication ;
- ( 10 ) Drug distribution.

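### Comparability of the arms is judged only by significance tests, which do not measure imbalance, while the HAMD-24 model names no age term and leaves the role of baseline PSQI unclear

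*Combined protocol and SAP*

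**What the plan says.** Section X.2(2), on comparability, says that "Demographic data and other basic indicators were compared to measure the comparability of the two groups". The methods that follow are all hypothesis tests: a chi-square "test or exact probability method, CMH test, t test, variance analysis or non-parametric statistical method were used". Section X.2(6) applies one criterion to every test: P≤0.05 "indicated that the difference was statistically significant". The plan gives no list of baseline variables, no measure of the size of a difference, and no consequence of a significant or non-significant result.

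For efficacy, section X.2(4) offers repeated measures or, as an alternative, regression: "linear regression models were used to control baseline depression scores or sleep scores". It adds a t test on change from baseline, which has no covariates. Age appears in none of these analyses, although section 4.1 admits patients "18-80 years old". Baseline PSQI is available, because section 7.1 lists "PSQI scale evaluation" at week 0.

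Section 5.1 sets "200 cases in the experimental group and 100 cases in the control group".

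**The concern.** A baseline p value depends on the sample size as well as on the difference, and it takes no account of whether the variable predicts HAMD-24. It is therefore a poor measure of comparability in both directions. A difference in a strongly prognostic variable can stay above 0.05, and a trivial difference in an irrelevant variable can fall below it by chance.

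The second half of the concern is in section X.2(4). What protects an estimate from baseline imbalance is a set of covariates fixed in advance, and the plan is loose there. The regression is optional, the change-score t test has no covariates, age is not named, and the "linear regression models were used to control baseline depression scores or sleep scores" wording does not say which baseline score enters which model. With the covariates left open and no rule tied to the baseline tests, nothing in the plan prevents those tests from guiding the choice of covariates. At stake are some precision in the D90 HAMD-24 comparison and the clarity of the baseline report.

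**Working it through.** **Inputs from the documents.** Arms of 200 and 100 (section 5.1); P≤0.05 for all tests (X.2(6)). Sidedness is not stated, so two-sided is assumed.

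**The plan's own figure.** Section 5.1 says: "It is assumed that the case shedding rate is 15 %, and the sample size is not less than 117 pairs". Starting from 100 pairs, 100/0.85 = 117.6, which agrees with 117 apart from rounding (118 if rounded up). The final 300 is larger than either, and this point does not dispute it. The plan states no imbalance threshold or false-flag rate to reproduce.

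**1. Smallest observed difference that reaches significance, continuous variable.**
- SE of a standardised difference = √(1/200 + 1/100) = 0.1225.
- Threshold = 1.96 × 0.1225 = 0.240 SD (0.241 with the t distribution on 298 df).
- If the tests were run only on patients remaining after 15% dropout (170 and 85), it would be 1.96 × √(1/170 + 1/85) = 0.26 SD.
- For a binary variable, the threshold is 0.240 × √(p(1−p)): about 12 percentage points at p = 50% and 7 points at p = 10%.

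**2. Sensitivity of the test.** If the groups truly differed by 0.2 SD, the test would reach P≤0.05 about 37% of the time. This applies only if allocation can produce real differences; under proper randomisation there are none.

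**3. Chance flags under proper randomisation.** With k independent tests, the probability of at least one P≤0.05 is 1 − 0.95^k. The plan does not state k, so a range is shown.

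| k | At least one P≤0.05 |
|---|---|
| 4 | 19% |
| 5 | 23% |
| 10 | 40% |
| 15 | 54% |

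Correlation lowers these rates. By simulation, the range for 10 to 15 tests falls to about 35–46% at pairwise correlation 0.3, and to about 29–36% at 0.5.

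**4. What fixed adjustment is worth.** The documents give no prognostic strength for PSQI or age. Assume that together they explain R² = 3–10% of the D90 HAMD-24 variance left after baseline HAMD-24, with SD in this step meaning the SD of that remaining variation.
- Equivalent gain in patients = 1/(1 − R²) − 1: 1/0.97 − 1 = 3.1%; 1/0.90 − 1 = 11.1%.
- Implied correlation = √R²: √0.03 = 0.173; √0.10 = 0.316.
- Shift in the treatment contrast per 0.2 SD of observed imbalance in the combined PSQI-and-age predictor = 0.2 × √R²: 0.2 × 0.173 = 0.035 SD; 0.2 × 0.316 = 0.063 SD.
- Relative to the SE of 0.1225: 0.035/0.1225 = 0.3 and 0.063/0.1225 = 0.5.

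**The case against.** Several stronger readings are tempting, and the documents do not support them.

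- A reader might infer that the plan declares any imbalance under 0.24 SD comparable. It does not say so. That label is an inference from the stated purpose and the P≤0.05 criterion, and 0.24 SD applies to continuous variables only.
- A reader might take 40–54% as the false-flag rate for this trial. It requires 10 to 15 independent tests, which the plan does not specify. Section 4.1 admits only women of Han nationality, so sex and ethnicity cannot differ. If only age, BMI, HAMD-24 and PSQI were tested, the figure would be 19%.
- A reader might say that baseline PSQI is left out of the HAMD-24 model. The wording is ambiguous: PSQI is unspecified, not excluded.
- A reader might put the shift at 0.06–0.10 SD, by applying correlations of 0.3–0.5 to a 0.2 SD imbalance. Once baseline HAMD-24 is in the model, only the association that remains counts. On the 3–10% assumption the shift is 0.035–0.063 SD. Under proper randomisation it is chance variation that the confidence interval already covers, not bias.

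Two further objections carry weight. Nothing in the documents shows that age or PSQI predicts D90 HAMD-24, so their choice is a judgement. Also, section X.2(4) names no primary analysis among its several options, which is a larger problem that this point does not settle.

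One possible defence of the tests is that section XI.1 forms groups by enrolment order and draws lots only for the group letters, so baseline differences may not be pure chance. Even so, a test that detects a true 0.2 SD difference only 37% of the time gives little reassurance. The size of each difference is more informative.

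**Conclusion.** The point holds as a minor one. Section X.2(2) measures comparability only by significance tests, and those tests do not do that job: differences below about 0.24 SD in a continuous variable go unflagged at 200:100, and chance flags range from 19% to 54% for 4 to 15 independent tests. Section X.2(4) names age nowhere and leaves the role of baseline PSQI in the HAMD-24 model unclear.

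Dropping the baseline p values would not by itself change any efficacy result. The practical gain comes from fixing the covariates: about 3–11% more patients' worth of information, and removal of a shift of about 0.3 to 0.5 SE per 0.2 SD of observed imbalance. Both figures rest wholly on the assumed 3–10% of remaining variance. The threshold and the chance-flag rates rest on two-sided tests, and the latter also on independence and proper randomisation.

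**What to change.** **Section X.2(2).** Report baseline values by arm with standardised differences and no tests. State that baseline p values will not be used to judge comparability or to choose covariates.

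**Section X.2(4).** Before unblinding, fix the D90 HAMD-24 regression with baseline HAMD-24, baseline PSQI and age as covariates, whatever imbalance is observed. Use the same three covariates for D90 PSQI.

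**Cost.** SAP wording and two extra model degrees of freedom with about 255 (300 × 0.85) to 300 patients. The scales are already scheduled at week 0 and age comes with the demographic data, so no new data collection is needed.

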### 4.3 rejecting standard

- ( 1 ) After enrollment, it was found that the included objects did not meet the inclusion criteria ;

---

( 2 ) Subjects who did not take oral ganoderma lucidum spore powder or intervene in the course of dissatisfaction after enrollment according to the study protocol ;

( 3 ) poor compliance, midway active withdrawal or lack of main indicators, incomplete data, etc., can not determine the efficacy or safety.

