## 3. Emergency Blinding

When the patient has serious adverse reactions or emergency events need to determine the group for treatment, when the patient has serious complications or symptoms of deterioration must take emergency measures, emergency cases do need to break the blind, by the researchers in the center of the person in charge, the person in charge after consultation with the bidding unit can read the emergency letter to break the blind. Once the corresponding numbered emergency letter is opened, the case is treated as a shedding case.

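### Several HAMD-24 tests and two analysis sets are planned for efficacy and none is named primary, so nothing fixes which result decides the trial

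*Combined protocol and SAP*

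**What the plan says.** Section 8.1 names HAMD-24 as the leading indicator, and its validity standard is a fall in score after 90 days of treatment. HAMD-24 is scored at baseline, D28 and D90 (sections 7.1–7.3).

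Section X.2(4) gives three routes to a comparison between arms:

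- "Repeated measures were used to compare the differences in measurement data such as depression scores and sleep scores", without saying whether the group effect, the group-by-time effect or a D90 contrast is meant;
- "or linear regression models were used to control baseline depression scores or sleep scores", without naming the visit;
- an instruction to "use the t test to compare the difference between the score changes of the experimental group and the control group".

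Section X.2(6) applies P ≤ 0.05 to all tests, with no hierarchy and no adjustment.

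On the analysis sets, section X.1(1) uses the FAS for efficacy, and there "the missing data was filled with the last observed data filling ( LOCF ) criterion". Section X.1(2) adds: "The PPS set is used for efficacy analysis". Neither set is ranked above the other. The FAS is described as cases "randomized into groups and at least 1 month after surgery, that is, Intention-to-treat". Section 4.3 separately rejects enrolled patients for "poor compliance, midway active withdrawal or lack of main indicators, incomplete data, etc., can not determine the efficacy or safety", without saying which analysis set that affects.

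**The concern.** The scale and the time point are fixed, but the deciding comparison is not. Three approaches in two sets give six candidate HAMD-24 results, more if repeated measures is read both as a group effect and as group-by-time. These can disagree. The plan has no rule for that case and does not rule out claiming success on whichever result is significant. If that happened, a reported P ≤ 0.05 could not be read as a 5% test.

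The options also differ in what they estimate. A group main effect over all three visits averages in the baseline score, where randomised arms do not truly differ, so it dilutes a benefit seen at D90. A sponsor who settled on that reading could miss a benefit that the other tests would usually detect.

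**Working it through.** **The plan's own figure.** Section 5.1 inflates 100 pairs for 15% loss: 100/(1 − 0.15) = 117.6, which matches the stated 117 when truncated. The final 300 (200:100) rests on no effect size, SD or power, so there is no planned power to reproduce.

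**Inputs.** From the documents: 200 and 100 patients and 15% loss, giving 200 × 0.85 = 170 and 100 × 0.85 = 85 evaluable; three HAMD-24 visits; entry score 8–20; threshold 0.05. Assumed, because the documents do not give them: SDs of 3.2/4.7/5.0 at baseline/D28/D90 (baseline narrowed by the entry range), a common correlation ρ of 0.3, 0.5 or 0.7 between visits, and two-sided testing.

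**False-positive rate with no true effect** (simulated, 20,000–40,000 trials per correlation, 170/85; group-by-time is the multivariate 2-df test):

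| What counts as success | ρ = 0.3 | ρ = 0.5 | ρ = 0.7 |
|---|---|---|---|
| Any single test fixed in advance | about 5% | about 5% | about 5% |
| Regression or change t test | 6.6% | 5.5% | 5.2% |
| Those two or group-by-time | 8.9% | 8.0% | 7.9% |
| Those three or group main effect | 12.4% | 11.7% | 11.5% |

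Varying the baseline SD from 2.5 to 4.0 gives 4.9–7.2% for the second row and 11.0–13.2% for the last.

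**Choice of set.** Take one regression read in either set, with an FAS of 200/100, 15% loss and LOCF (30,000 trials per correlation). The rate is 6.0–6.7% if the PPS is 170/85 and 6.9–7.3% if it is 150/75.

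**Power**, for an assumed 2-point D90 benefit in 170/85 completers. The standard error is SD × √(1/170 + 1/85) = SD × 0.1328.

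- Regression: SD = 5.0 × √(1 − ρ²). At ρ = 0.3 this is 4.77, so SE = 0.634 and power is 88.2%. At ρ = 0.5 and 0.7 power is 93.4% and 98.7%.
- Change t test: SD = √(s₀² + 25 − 2ρ × 5s₀), with s₀ the baseline SD. At s₀ = 3.2 and ρ = 0.3 this is √25.64 = 5.06, and power is 84.2%. At s₀ = 4.0 and ρ = 0.3 it is √29 = 5.39, and power is 79.5%.
- The gain from regression is therefore 88.2 − 84.2 = 4.0 points in the first case and 88.2 − 79.5 = 8.7 in the second. Over s₀ of 2.5–4.0 and all three correlations it runs from about 0 to 9 points.
- Group main effect: with half the benefit present at D28, the averaged difference is (0 + 1 + 2)/3 = 1.0 point. Power is 66%, 57% and 49% for ρ = 0.3, 0.5 and 0.7. With no benefit at D28 it is 35%, 29% and 25%.
- Group-by-time: with the full benefit already present at D28, power is 92.5%, 97.6% and 99.8%, which is 4.3, 4.2 and 1.1 points above regression.

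These power figures are for completers. In an FAS of 200/100 with LOCF, losses after D28 and no D28 benefit, regression power is about 83–97%.

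**Does regression answer section 8.1?** If D90 = a + b·arm + c·baseline, then D90 − baseline = a + b·arm + (c − 1)·baseline. The arm coefficient b is the same, so the adjusted analysis also compares the fall in score.

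**The case against.** The strongest reply is that the documents narrow the choice considerably. HAMD-24 and 90 days are named, and the change-score t test is the only one of the three not offered as an alternative; it also matches the section 8.1 standard most directly. That is a fair case for the t test as the implied primary. But no sentence says so, and all three tests share one paragraph and one threshold. It follows that any single named test would protect the 5% level, so the preference for regression is secondary to the need to name one.

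The largest error rate is also conditional. It needs the group main effect to count, which the plan never names and which is only one reading of repeated measures. Without it the figure is 8–9%.

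A reader might go further on the FAS, and the documents do not support it:

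- That LOCF is undecided for the primary analysis. Section X.1(1) already applies it to FAS efficacy analyses. Whether LOCF is a good method is a separate question.
- That patients unblinded in an emergency leave the FAS. Section XI.3 says only that "the case is treated as a shedding case"; it does not remove anyone from the set.
- That the one-month condition contradicts intention-to-treat. It may simply describe the enrolled population, and if it is met before randomisation there is no conflict.

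The section 4.3 rejections are the stronger point. Even there, section X.1 puts compliance and completeness in the PPS definition only, so one clarifying line is enough.

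**Conclusion.** The concern holds and should be fixed before unblinding. No HAMD-24 test, repeated-measures effect or analysis set is designated as deciding the trial. That gap is plain from the text and depends on no simulated number.

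Its size depends on conduct. There is no inflation if one test and set are fixed in advance. If the choice follows the results, or any significant result counts, the rate is about 5–7%, 8–9% or up to about 12%, according to which tests count, under the SDs, correlations and 170/85 stated above. It would be wrong to infer that the trial as planned has a 12% error rate: the plan permits that outcome but does not prescribe it.

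**What to change.** Before the blind envelope is opened, amend X.1 and X.2(4) as follows.

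1. Name one primary analysis: the D90 HAMD-24 difference between arms from linear regression adjusted for baseline HAMD-24, in the FAS of all randomised patients as randomised, at two-sided 0.05, reported with the estimate and 95% CI.
2. Label repeated measures (with its effect named), the change-score t test and the PPS as sensitivity analyses that do not decide success.
3. Add one line that section 4.3 rejections affect the PPS only, and that the one-month-after-surgery condition applies before randomisation and is not a later exclusion.

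Regression is preferred because it uses a baseline score already collected and gains about 0–9 power points over the change t test under the assumptions above. No new data, visits or patients are needed. The price is giving up the choice among tests, and about 1–4 points of power against group-by-time if the full benefit has appeared by D28.
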